#### **EP and TP analysis groups**

The EP/TP analysis groups are defined according to the patient's fibrosis status and genotype/subtype and standard summaries are structured as follows:

- Total (regardless of cirrhosis status)
  - (1) Total (regardless of genotype)
  - (2) G1 (Total)
  - (3) G1a (including mixed G1 subtypes and patients with G1 unknown subtype)
  - (4) G1b
  - (5) G4 (non-G1)
  - (6) Other/unknown genotype (only for EP)
- Patients with cirrhosis
  - (7) Total (regardless of genotype)
  - (8) G1 (Total)
  - (9) G1a (including mixed G1 subtypes and patients with unknown G1 subtype)
  - (10) G1b
  - (11) G4 (non-G1)
  - (12) Other/unknown genotype (only for EP)
- Patients without cirrhosis
  - (13) Total (regardless of genotype)
  - (14) G1 (Total)
  - (15) G1a (including mixed G1 subtypes and patients with unknown G1 subtype)
  - (16) G1b
  - (17) G4 (non-G1)
  - (18) Other/unknown genotype (only for EP)
- · Patients with unknown fibrosis status
  - (19) Total (regardless of genotype)
  - (20) G1 (Total)
  - (21) G1a (including mixed subtypes and patients with unknown subtype)
  - (22) G1b
  - (23) G4 (non-G1)
  - (24) Other/unknown genotype (only for EP)

(HCV genotypes will be combined as follows: G1 [total], G1a\*, G1b, G4 [non-G1]. \* includes mixed or other G1 subtypes and patients with unknown G1 subtypes.

Most recent stage of liver fibrosis will be categorized as follows: No cirrhosis/Transition to cirrhosis, Cirrhosis. Only one method should be selected by the physicians to report stage of fibrosis. Nevertheless, if there are multiple answers the following priority will be used: :

- 1. Biopsy,
- 2. Non-invasive,
- 3. Clinical/best guess.

For biopsy as assessment method the respective categories are defined as follows:

- "No cirrhosis" is defined by "No fibrosis", "Mild/minimal fibrosis", "Moderate fibrosis"
- "Transition to cirrhosis" is defined by "Advanced Fibrosis"
- "Cirrhosis" is defined by "Cirrhosis".)

#### CP analysis groups and related treatment regimens

The CP analysis groups are defined according to the patient's fibrosis status and genotype/subtype. The standard summaries by CP analysis groups in the CP and CPSFU population are structured follows (is not specified otherwise):

- Total (regardless of cirrhosis status)
  - (1) Total (regardless of genotype)
  - (2) G1 (Total)
  - (3) G1a (including mixed subtypes and patients with unknown subtype)
  - (4) G1b
  - (5) G4 (non-G1)
- Patients with cirrhosis
  - (6) Total (regardless of genotype)
  - (7) G1 (Total)
  - (8) G1a (including mixed subtypes and patients with unknown subtype)
  - (9) G1b
  - (10) G4 (non-G1)
- Patients without cirrhosis
  - (11) Total (regardless of genotype)
  - (12) G1 (Total)
  - (13) G1a (including mixed subtypes and patients with unknown subtype)
  - (14) G1b
  - (15) G4 (non-G1)

#### SP analysis groups

The SP analysis groups are defined according to the treatment regimen and patient's fibrosis status. The standard summaries by SP groups in the safety population are as follows (if not specified otherwise):

- Total (regardless of cirrhosis status)
  - (1) Total
  - (2) 2DAA w/o RBV
  - (3) 2DAA + RBV
  - (4) 3DAA w/o RBV
  - (5) 3DAA + RBV
- Patients with cirrhosis
  - (6) Total
  - (7) 2DAA w/o RBV
  - (8) 2DAA + RBV
  - (9) 3DAA w/o RBV
  - (10) 3DAA + RBV
- Patients without cirrhosis
  - (11) Total
  - (12) 2DAA w/o RBV
  - (13) 2DAA + RBV
  - (14) 3DAA w/o RBV
  - (15) 3DAA + RBV
- · Patients with unknown fibrosis status
  - (16) Total
  - (17) 2DAA w/o RBV
  - (18) 2DAA + RBV
  - (19) 3DAA w/o RBV
  - (20) 3DAA + RBV

(2DAA - paritaprevir/r-ombitasvir, 3 DAA - paritaprevir/r-ombitasvir + dasabuvir, RBV – ribavirin taken, w/o RBV – no ribavirin taken)

# **NCP** analysis groups

The summary tables for the NCP will only show the data pooled for all patients in the NCP without any subgrouping by genotype and/or fibrosis status.

# 4.2.2 Definition of Baseline and Visit Time Windows

This observational study covers three documentation periods, see Figure 1. An overview of data to be collected throughout the study is summarized in Table 2.

**Table 2 - Data Documentation Schedule** 

Assessment/ Procedure		Treatment Period		Post-treatment (PT) Period			
(only available data to be collected; no diagnostic or monitoring procedures to be applied to the patients apart from those of routine clinical practice)	Baselin	On- treatment visits	Mid treatment visit for pts receiving 24 weeks of therapy	EoT b	Early PT visit	SVR 12 visit	SVR 24 visit
Patient authorization	X a						
Demographic information	Χ						
IL28B	Χ						
Relevant CHC disease characteristics	Х						
Liver fibrosis stage	Х						
CHC treatment history	Χ						
HCV genotype and subtype	Χ						
HCV RNA samples	Х	Х	Х	Х	Х	Χ	Χ
Clinical chemistry and hematology	Χ	Х	Χ	Х	Х	Х	Х
ABBVIE REGIMEN initiation documentation	Х						
ABBVIE REGIMEN adherence		Х	Χ	Х			
Concomitant medication	Χ	Х	Χ	Χ			
Relevant medical history, co-morbidities	Χ						
sAE, AE and pregnancy reporting	Х	Х	Х	Х	Xc	$X_q$	Xd
For patients receiving RBV: Evidence, in accordance with local label, that female patient or female partner of male patient is not pregnant	Х						
Patient questionnaires – WPAI, EQ5D-5L	Χ			Х		X	Х

Abbreviations: EoT = End of Treatment (at Week 12 or 24 or at premature discontinuation), PT = Post-Treatment

- a Written patient authorization must be obtained before any data documentation in the eCRF
- b Patients who prematurely discontinue should return to the site to document EoT data
- c Tolerability documentation until PT week 4
- d Pregnancy reporting for patients treated with DAA plus RBV

In accordance with the non-interventional nature of the study all HCV RNA measurements will be performed at the sole discretion of the physician and all HCV RNA measurements have to be entered into the eCRF. All recorded HCV RNA values will be assigned to appropriate time points (baseline, on-treatment visits, EoT visit, post-treatment visits) as follows:

Table 3 - Analysis Time Windows for HCV RNA

Phase	Time point	Time Window
Pre-Treatment	Baseline	Last value prior to start of study treatment (i.e.
		≤study day 1)
On-treatment		Study day during treatment period^#
		(Study day 1 = first treatment day)
Treatment Week	4 (RVR*)	15 - 42^
EoT	Actual EoT	Study day of last dose#
		(28 days prior to last dose - 7 days post last
		dose)
Post Treatment	12 weeks (SVR 12	>=70-126 days post last dose
	window)	
	24 weeks (SVR24	127-210 days post last dose
	window)	

^values must also be <= 7 days post last dose

#>=study day 2

\*RVR = rapid virological response

All reported safety laboratory test results will be assigned to one of the time points using the time windows specified in the table below.

Table 4 - Analysis Time Windows for Safety Laboratory Data

Phase	Time point	Time Window
Pre-Treatment	Baseline	Last value prior to start of study treatment (i.e.
		≤study day 1)
		Study day during treatment period
		(Study day 1 = first treatment day)
Treatment Weeks	4 (day 29)	15 – 42^
	8 (day 57)	43 – 70^
	12 (day 85)	71 – 98^
	16 (day 113)	99 – 126^
EoT	Actual EoT	Study day of last dose#
		(28 days prior to last dose - 7 days post last
		dose)
Post Treatment 4 weeks 8– 56 pc		8– 56 post last dose
	(28 days post last	
	dose)	
	12 weeks	57 – 126 days post last dose
	(84 days post last	
	dose)	
	24 weeks	127 – 252 days post last dose
	(168 days post last	
	dose)	

^values must also be <= 7 days post last dose

#>=study day 2

# 4.2.3 Handling of missing data

No data will be imputed for any effectiveness or safety analyses except for the analyses of the HCV RNA endpoints and certain PRO endpoints. The discussion of missing data imputation for the PRO endpoints is included in section 4.2.7.2.3.

HCV RNA values will be selected for an RVR, EOTR and SVR analysis based on visit windows as defined in Table 3. When there is no HCV RNA value in a visit window based on defined visit windows, the closest values before and after the window, regardless of the value chosen for the subsequent and preceding window, will be used for the flanking imputation described below. For analysis of RVR, EOT and SVR, if a subject has a missing HCV RNA value at a post-Day 1 visit but with undetectable or unquantifiable (≤50 IU/mL) HCV RNA levels at both the preceding value and succeeding value, the HCV RNA level will be considered undetectable or unquantifiable,

respectively, at this visit for this subject. In addition, if a subject has an unquantifiable HCV RNA level at the preceding value and an undetectable HCV RNA level at the succeeding value, or vice versa, the HCV RNA level will be imputed as unquantifiable at this visit for this subject.

For analyses of RVR, subjects still missing a value for the visit after flanking imputation will be imputed as a failure. For EoTR and SVR analysis, if there is no value in the appropriate window after flanking imputation but there is an HCV RNA value after the window, then it will be imputed into the EoTR or SVR window respectively. Subsequent to this flanking imputation, if a subject is missing a value for the visit window associated with the analysis, the subject will be imputed as a visit failure (i.e., not undetectable or unquantifiable).

If a subject starts another treatment for HCV, then all HCV RNA values for this subject measured on or after the start date of the new HCV treatment will be excluded from analyses. The subject will be considered a failure for summaries of viral response at all time points after the start of the new HCV treatment.

Due to the non-interventional nature of this study several different methods for determination of the HCV RNA value can be applied. For the purpose of the statistical analysis, a HCV RNA measurement is considered ≤50 IU/mL.

- if a PCR test was used
- and the test result is undetectable and the LLoD of the test is ≤50 IU/mL or the test result is unquantifiable (i.e. detected but below LLoQ) and the LLoQ is ≤50 IU/mL

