9.4.1.3 Post-Treatment Documentation

Follow-up visits are scheduled by the physician per routine clinical practice. Likewise treatment, procedures and diagnostic methods will follow physicians' routine clinical practice.

The following will be documented:

- Laboratory data

- Key clinical chemistry

- ALT
 - AST

- Remarks

- including ULN
including ULN,
APRI and FIB-4, will be calculated

- γ -GT
 - Total bilirubin
 - Albumin
 - Creatinine

- creatinine clearance will be calculated

- Key hematology

- Hb
 - Platelets
 - Prothrombin time

- or INR

- Virology

- HCV RNA

- quantitative/ qualitative HCV RNA PCR test, see 9.4.1.4

- HIV-infected patients only

- CD 4 count
 - HIV RNA

- most recent assessment
in copies/mL

- Tolerability (sAEs, see 0) and pregnancies (see 0)
- Patient questionnaires see 9.4.1.6

Confidential Information

No use or disclose outside AbbVie is permitted without prior written authorization from AbbVie

Table 2 - Data Documentation Schedule

Assessment/ Procedure (only available data to be collected; no diagnostic or monitoring procedures to be applied to the patients apart from those of routine clinical practice)	Baseline	Treatment Period			Post-treatment (PT) Period		
		On-treatment visits	Mid treatment visit for pts receiving 24 weeks of therapy	EoT ^b	Early PT visit	SVR 12 visit	SVR 24 visit
Patient authorization	X ^a						
Demographic information	X						
IL28B	X						
Relevant CHC disease characteristics	X						
Liver fibrosis stage	X						
CHC treatment history	X						
HCV genotype and subtype	X						
HCV RNA samples	X	X	X	X	X	X	X
Clinical chemistry and hematology	X	X	X	X	X	X	X
ABBVIE REGIMEN initiation documentation	X						
ABBVIE REGIMEN adherence		X	X	X			
Concomitant medication	X	X	X	X			
Relevant medical history, co-morbidities	X						
sAE, AE and pregnancy reporting	X	X	X	X	X ^c	X ^d	X ^d
For patients receiving RBV: Evidence, in accordance with local label, that female patient or female partner of male patient is not pregnant	X						
Patient questionnaires – WPAI, EQ5D-5L	X			X		X	X

Abbreviations: EoT = End of Treatment (at Week 12 or 24 or at premature discontinuation), PT = Post-Treatment

- a Written patient authorization must be obtained before any data documentation in the eCRF
- b Patients who prematurely discontinue should return to the site to document EoT data
- c Tolerability documentation until PT week 4
- d Pregnancy reporting for patients treated with DAA plus RBV

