9.4.1.5 Concomitant Medication

Concomitant medication - the following will be documented:

- Concomitant medication used from the time when the decision is made to initiate treatment with the ABBVIE REGIMEN until after the last dose

It should be verified by the treating physician that concomitant medication can be safely administered with the ABBVIE REGIMEN (including ritonavir) and RBV. Some medications may be contra-indicated, some may require dose adjustments due to potential for drug-drug interactions (DDIs). The investigator or qualified designee should review the concomitant medication(s) labels and screen concomitant medications at each visit for potential DDIs.

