9.6 Data Management

9.6.1 Electronic Case Report Forms

Data for this study will be recorded in English by each participating center via an electronic data capture (EDC) system using a web-based eCRF. Examinations, diagnostic measures, laboratory assessments, findings and observations routinely performed in patients with CHC included in this cohort, will be transcribed by the investigator or designee from the source documents into the eCRF. Only data specified in the protocol will be entered into the eCRF. For each enrolled patient, the investigator or designee will create a new patient file in the eCRF and a unique patient number will be automatically allocated by the system.

A comprehensive data validation program utilizing front-end checks in the eCRF will validate the data. Automated checks for data consistency will be implemented, discrepancies need to be solved by the researcher in the eCRF before the module can be completed.

Follow-up on eCRF data for medical plausibility will be done by AbbVie personnel (or their representatives). Queries will be generated in the eCRF for online resolution at the site. The investigator or an authorized member of the investigator's staff will make any necessary data corrections to the eCRF. All change information, including the date and person performing the corrections, will be available via the audit trail, which is part of the EDC system. The principal investigator of each site will finally review the eCRFs for completeness and accuracy of available data and provide his or her electronic signature and date to the eCRFs as evidence thereof.

Access to the EDC system will be provided for the duration of the study through a password-protected method of internet access. Such access will be removed from investigator sites at the end of the site's participation in the study. Data from the EDC

Confidential Information

No use or disclose outside AbbVie is permitted without prior written authorization from AbbVie

system will be archived on appropriate data media (e.g. CD-ROM) and provided to the investigator as a durable record of the site's eCRF data.

Original Questionnaires will be sent from the participating site to:

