9.7 Data Analysis

9.7.1 Analysis Population, Time Windows and Handling of Missing Data

The target population (TP) is defined as all patients who fulfill the criteria specified in Section 9.2.1. The core population (CP) is defined as all patients of the TP, who have started the treatment combination recommended in the current local label for their disease characteristics. Patients not receiving the treatment recommended in the local label will be summarized in the non-core population (NCP). In addition, the core population with sufficient follow-up data (CPSFU) is defined as all CP patients, who fulfil one of the following criteria:

- (1) evaluable HCV RNA data ≥ 70 days after the last actual dose of the ABBVIE REGIMEN (i.e. data within the SVR12 time window)
- (2) a HCV RNA value ≥ 50 IU/mL at the last measurement post-baseline (i.e. no virological response achieved at the last measurement on-treatment or post-treatment)
- (3) HCV RNA < 50 IU/mL at the last measurement post-baseline, but no HCV RNA measurement ≥ 70 days after the last actual dose of the ABBVIE REGIMEN due to reasons related to safety (e.g. dropped out due to AE) or incomplete efficacy information (e.g. virologic failure such as relapse is reported in the eCRF but date and value of the corresponding HCV RNA test

Confidential Information

is missing). This means only patients who had virological response at their last on-treatment or post-treatment measurement, but had no HCV RNA measurements ≥ 70 days post-treatment for reasons not related to safety or effectiveness (e.g. lost-to-follow-up or patient not willing to perform an additional HCV RNA test ≥ 70 days post-treatment) will be excluded from this analysis.

The Safety Population (SP) is defined as all patients who received at least one dose of the ABBVIE REGIMEN.

In accordance with the non-interventional nature of the study all HCV RNA measurements will be performed at the sole discretion of the physician and all HCV RNA measurements have to be entered into the eCRF. All recorded HCV RNA values will be assigned to appropriate time points (baseline, on-treatment visits, EoT visit, post-treatment visits). The time windows for the assignments will be specified in the statistical analysis plan (SAP).

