No data will be imputed for any effectiveness or safety analyses except for the analyses of the HCV RNA endpoints. When there is no HCV RNA value in a visit time window post-baseline, but prior to EoT, the closest values before and after the window, regardless of the value chosen for the subsequent and preceding window, will be used for the flanking imputation described below. If a patient has a missing HCV RNA value at a post-baseline visit prior to EoT but has undetectable HCV RNA (with LLoD ≤ 50 IU/mL) or unquantifiable, but detectable HCV RNA levels (with LLoQ ≤ 50 IU/mL) at both the preceding and succeeding measurements, the HCV RNA level will be considered undetectable or unquantifiable, respectively, at this visit for this patient. In addition, if a patient has an unquantifiable HCV RNA level at the preceding measurement and an undetectable HCV RNA level at the succeeding measurement, or vice versa, the HCV RNA level will be imputed as unquantifiable at this visit for this patient. For virological response at EoT a corresponding backward imputation approach will be applied. This means if HCV RNA is missing at EoT, then unquantifiable or undetectable will be assumed for EoT, if the succeeding HCV RNA value is undetectable or unquantifiable. For SVR12 the single last available HCV RNA measurement ≥ 70 days post-treatment will be used. Subsequent to this flanking and backward imputation, if the HCV RNA value remains missing at a specific time point, then the patients will be considered as virological failure at this time point (i.e. not undetectable or unquantifiable).

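### SAP 4.2.3 depends on the start date of any new HCV treatment, but the protocol specifies no such item after end of treatment, so a retreated relapser can count as an SVR24 responder and, less often, an SVR12 responder

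*SAP*

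**What the plan says.** **The rule.** SAP 4.2.3 has a sentence that begins: "If a subject starts another treatment for HCV, then all HCV RNA values for this subject measured on or after the start date". Values from that date onward are dropped. It adds: "The subject will be considered a failure for summaries of viral response at all time points after the start of the new HCV treatment". So the rule both removes values and imputes failure. The protocol has no rule of its own on new HCV treatment.

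**What is specified for collection after EoT.** The post-treatment list in protocol 9.4.1.3 covers laboratory data, HCV RNA, tolerability, pregnancies and questionnaires. In Table 2 of both documents the row "Concomitant medication" is marked at baseline, on treatment, mid-treatment and EoT. It is not marked at the early post-treatment, SVR12 or SVR24 visits. CHC treatment history is marked at baseline only. Protocol 9.4.1.5 asks for "Concomitant medication used from the time when the decision is made to initiate treatment with the ABBVIE REGIMEN until after the last dose" and names no follow-up period. Protocol 9.6.1 adds: "Only data specified in the protocol will be entered into the eCRF".

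**What is still collected.** Protocol 9.7.1 requires that "all HCV RNA measurements have to be entered into the eCRF". That includes values measured during retreatment.

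**How SVR is assigned.** SAP 4.1.1 and SAP Table 3 set the SVR12 window at days 70-126 and the SVR24 window at days 127-210 after the last dose. Under SAP 4.2.3, a window still empty after flanking imputation is filled with a later value if there is one. The protocol's rule for choosing among values is "For SVR12 the single last available HCV RNA measurement ≥ 70 days post-treatment will be used". The SAP adds the upper bound of 126 days but does not say which of several in-window values counts.

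**The concern.** The sponsor has already decided that viral suppression under another HCV therapy must not count as a response to this regimen. If the start date is not captured, that decision cannot be carried out after EoT, and the negative values obtained on retreatment go into the analysis as ordinary follow-up.

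The error runs one way. With the date, the patient is a failure. Without it, the only possible change is from failure to success. The primary rate is affected to a limited extent and SVR24 more so. SVR24 is also the outcome of the predictor and adherence regressions in SAP 4.2.7.2.1, where failures are the scarce events.

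**Working it through.** **Step 1. Trace the rules.** The four records below are illustrative, and all four patients start another HCV treatment after EoT. Results are shown with the start date known and unknown.

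| Patient | HCV RNA after last dose | Date known | Date unknown |
|---|---|---|---|
| A | >=50 IU/mL at week 4, retreated, <50 later within days 70-126 | SVR12 failure | SVR12 responder |
| B | >=50 at week 4, retreated, no test in days 70-126, <50 on day 150 | SVR12 and SVR24 failure | SVR12 and SVR24 responder |
| C | only in-window value >=50, retreated, <50 in days 127-210 | failure at both | SVR12 failure, SVR24 responder |
| D | stopped early with <50, switched, <50 in days 70-126, never positive | SVR12 failure | SVR12 responder |

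- In B, flanking does not apply because the preceding value is positive. The carry-back sentence then moves the day-150 value into the empty SVR12 window.
- C shows the limit of the SVR12 problem and why SVR24 is more exposed: SVR24 leaves more time for relapse, retreatment and suppression.
- If A also had a positive value inside the window, the result would depend on which in-window value is used. The protocol's choice is the last.
- The CPSFU sensitivity analysis (SAP 4.2.1) does not help, because a value from day 70 (or after day 126 for SVR24) is enough to place these patients in it.

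**Step 2. Reproduce the plan's precision.** The inputs, from protocol 9.5, are 400 enrolled with 90 to 95% evaluable, so n = 360 to 380, and SVR12 of 90% or 95%. The Clopper-Pearson limits are the 0.025 quantile of Beta(x, n-x+1) and the 0.975 quantile of Beta(x+1, n-x).

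| n | x | Limits (%) | Width | Protocol Table 3 |
|---|---|---|---|---|
| 360 | 324 (90%) | 86.43 to 92.90 | 6.47 | 6.5 |
| 360 | 342 (95%) | 92.21 to 97.01 | 4.80 | 4.8 |
| 380 | 342 (90%) | 86.53 to 92.83 | 6.29 | 6.3 |
| 380 | 361 (95%) | 92.30 to 96.96 | 4.66 | 4.7 |

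The table is reproduced. Half-widths run from 4.7/2 = 2.35 to 6.5/2 = 3.25 points. With the Wilson method of SAP 4.2.7.1 the widths at n = 360 are 6.22 and 4.58, which is close.

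**Step 3. Shift in SVR12.** With k misclassified patients the rate rises by 100 × k/n. The documents do not give k, so the values below are assumptions.

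| k (assumed) | n = 360 | n = 380 | 95% at n = 360 becomes | 90% at n = 360 becomes |
|---|---|---|---|---|
| 1 | 0.28 | 0.26 | 95.3% | 90.3% |
| 4 | 1.11 | 1.05 | 96.1% | 91.1% |
| 9 | 2.50 | 2.37 | 97.5% | 92.5% |

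At n = 360 and 95% there are 360 - 342 = 18 non-responders, and the half-width is 4.80/2 = 2.40. Eight patients give 8/360 = 2.22 points and nine give 2.50. So half of all non-responders would have to be misclassified to move the overall estimate by one half-width.

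**Step 4. Where one patient weighs more.** In a genotype-by-cirrhosis stratum of size m the shift per patient is 100/m. The documents give no stratum sizes; an assumed m of 20 gives 5 points. For the SVR24 regressions, if failures are as many as the planning figures imply (5% of 360 = 18 to 10% of 380 = 38, an assumption), each misclassified patient removes 1/38 = 2.6% to 1/18 = 5.6% of the events.

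**The case against.** **The field may exist.** The SAP analyses items that the protocol's data lists do not name: the method used to document adherence, the co-medication profiles, and CRF reasons for not completing the study. Profile B in SAP 4.2.8.2 even carries some post-treatment information, on earlier co-medication that is resumed. So protocol 9.6.1 does not prove that a retreatment date is missing. This stands. A reader might infer that the SAP rule cannot be applied at all. The documents support only that the protocol does not specify the item after EoT. A switch recorded up to EoT is within the collection period.

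**SVR12 is largely protected.** The SAP window replaces the protocol's open-ended last-value rule, so a negative value after day 126 matters only when the window is empty. A relapser whose only in-window value is >=50 IU/mL stays a failure. SAP 4.2.5 lists relapse among the reasons for having no HCV RNA from week 10, and such a patient is a failure by imputation if no later value exists. This also stands. The inference that the primary result is materially inflated is not supported.

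**Relapse is tabulated separately.** The week-4 relapser who completed treatment would still appear in the relapse table, so a cross-check would expose the conflict. That is true, but no stated rule says which classification prevails.

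**A SAP-only rule would do.** Letting any post-treatment value >=50 IU/mL fix later non-response would handle patients A to C. It would miss patient D, who switches without a positive value, and would leave the sponsor's own rule without its date.

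**Conclusion.** The point holds as a gap between a stated analysis rule and the data specified to support it. The main exposure is SVR24 and the regressions built on it. SVR12 is exposed by the narrower routes of a later in-window negative value or carry-back into an empty window. Each affected patient adds 0.26 to 0.28 points to SVR12 at n = 360 to 380, and the direction always favours the regimen. The total cannot be stated, because the documents give no retreatment frequency; for small counts the overall shift is well inside the planned half-width of 2.35 to 3.25 points. The conclusion assumes that the eCRF follows the protocol's lists and that some patients are retreated and tested within the 24-week follow-up, which routine care allows. If the eCRF already records new HCV treatment with dates through the SVR24 visit, what remains is to specify it in the protocol and to state the order of the SAP rules.

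**What to change.** 1. **Protocol 9.4.1.3 and Table 2:** add one item at the early post-treatment, SVR12 and SVR24 visits, recording any new anti-HCV treatment by name and start date, or none. For patients already past these visits, send a retrospective query to two groups: those with HCV RNA >=50 IU/mL at or after EoT followed by a negative value, and those who stopped the regimen early.
2. **SAP 4.2.3:** state that the new-treatment exclusion is applied before flanking imputation and carry-back, and that a later negative value is not carried back across an intervening post-treatment value >=50 IU/mL.

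The cost is one eCRF item already available in the chart, a short protocol amendment, two sentences in the SAP and a limited query round. No procedure or visit is added. The reported SVR may be slightly lower.
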